## 2.2 Secondary Objectives

- **2.2.1** To evaluate the overall survival (OS), which is defined as the time between date of registration and the date of death due to any cause. In analyzing the OS, it is important to take into account the MSKCC prognostic criteria defined by Motzer et. al. mRCC patients and compare the outcome in the appropriate risk categories [90].
- **2.2.2** To evaluate progression free survival (PFS), which is defined as the time between date of registration and the first date of documented disease progression or date of death due to any cause.
- **2.2.3** To evaluate time to progression (TTP), which is defined as time between date of registration and date of documented progression.
- **2.2.4** To evaluate the local control rate of irradiated lesions.
- **2.2.5** To evaluate median response duration, which is defined as the time between the date a response (CR or PR) was first seen until date of progression.
- **2.2.6** To measure treatment-related tumor-specific immune response.
- **2.2.7** To evaluate the tolerability and toxicity of this regiment as measured according to CTCAE v4.0.
- **2.2.8** To measure the improvement in health-related quality of life (HRQoL).

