The SABR prescription dose will be delivered to the periphery of the planning target volume (PTV, see below for definitions). Investigators will have discretion in choosing from either of the biologically equivalent dose levels using one or three fractions, although a single fraction is preferred over three fraction treatments. Treating physician will have further discretion in selecting the number and location of sites to treat if >6 sites of disease are present. Maximum number of lesions treated is deemed as feasible per the treating radiation oncologist. Physician's will be **REQUIRED** to leave at least one site of disease for the purpose of measuring a radiographic response (see section 6.1) at a non-treated site, as this is part of the primary endpoint. If left untreated, this site can be treated once patient meets the definition of progressive disease (PD) (see section 6). To clarify the definition of "site", each site is an area or organ with active extracranial disease (</=3 in the liver = one site and </=3 in the lung= one site) identified by CT scan, or PET/CT, within 4 weeks prior to initiation of SBRT (up to 2 contiguous vertebral metastasis will be considered a single site of disease). For example: a patient with 4 right axillary lymph nodes, L1-L2 bone metastasis, 3 right lung lesions, 1 left lung lesion, 2 liver lesions, and T2-T3 bone metastasis would be defined as having 6 sites of disease. Preference should be given to the largest feasible disease site, symptomatic sites and sites where palliative and preventative (i.e. to prevent a pathologic fracture in weight bearing bone, impending cord compression, impending SVC compression etc.) indications are applicable. The gross target/tumor volume (GTV) should be at least 2cm^3 in size, corresponding to roughly a 1.5 cm diameter tumor. This is to ensure that adequate tumor volume and therefore adequate tumor cells (roughly 10^8 -10^9 cells/cm^3 [96]) are killed for antigen presentation. Treating physicians should choose their dose based on established planning guidelines at their center including their ability to respect normal tissue tolerance listed below. It is not required that all targets be treated with the same dose fractionation. A dose from the following table should be used:

	Total Cumulative Dose Encompassing 95% of Planning					
	Target Volume (Gy)					
Number of	Protocol Compliant Minor Deviation * MinorDeviation					
Fractions						

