## 4.1.3.2 Normal Tissue Dose Constraints

In accordance with the prior Phase I studies [100], certain normal tissue dose constraints must be respected.

The possibility that SBRT-induced fibrosis might cause occlusion of large central airways, thus impeding ventilation distal to the occlusion has been well considered [101]. An adjustment to the fractionation scheme may be made if, in the opinion of the treating radiation oncologist, the following conditions apply: (1) the location of a lung lesion is close enough to a large proximal bronchial airway such that occlusion might occur, and (2) compromised ventilation to the segment(s) of lung potentially affected would cause clinically significant adverse consequences. In such a case, the treating radiation oncologist should discuss any proposed dose modifications with the PI to decide whether a regimen of similar biological potency can be safely given.

The same special condition applies in the setting of a patient whose primary prostate disease has been irradiated previously and is present as a site of disease; Since re-irradiation toxicity is a concern, these patients will be considered by the PI on a case-by-case basis and SBRT to a site previously irradiated with conventional fractionation within two years is not recommended. Re-irradiation to a site that has received previous SBRT is not allowed. Deviations from the intended dose regimen will be documented, with calculations of the BED of the applied regimen included in the patient's research chart along with documentation of the discussions pertaining to the idiosyncrasies of the case.

The following table lists the specific organ and dose fractionation constraints on normal tissues.

Serial Tissue	Volume	Volume Max (Gy)	Max Point Dose (Gy)**	Endpoint (≥Grade 3)
Optic Pathway	<0.2 cc	8 Gy	10 Gy	neuritis
Cochlea			9 Gy	hearing loss
Brainstem (not medulla)	<0.5 cc	10 Gy	15 Gy	cranial neuropathy
Spinal Cord and medulla	<0.35 cc <1.2 cc	10 Gy 8 Gy	14 Gy	myelitis
Spinal Cord Subvolume (5- 6 mm above and below level treated per Ryu)	<10% of subvolume	10 Gy	14 Gy	myelitis
Cauda Equina	<5 cc	14 Gy	16 Gy	neuritis
Sacral Plexus	<5 cc	14.4 Gy	16 Gy	neuropathy
Esophagus*	<5 cc	11.9 Gy	15.4 Gy	stenosis/fistula
Brachial Plexus	<3 cc	13.6 Gy	16.4 Gy	neuropathy
Heart/Pericardium	<15 cc	16 Gy	22 Gy	pericarditis
Great vessels	<10 cc	31 Gy	37 Gy	aneurysm

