#### 4.4 Duration of Follow Up

Subjects will be followed for ten years or death (although findings will be analyzed and reported at a median follow up of 2-4 years), whichever occurs first. Subjects removed from treatment for unacceptable adverse events will be followed until resolution or stabilization of the adverse event. The follow-up will be every 8 weeks (+/- 2 Weeks) from study registration with imaging studies and physical exam every 8 weeks for the first eight months, then every 12 weeks (+/- 2 Weeks) until two years, then every four months thereafter for a total of five years, and then every six months (+/- 1 month) for a total of ten years. See section 5.0 for detail.

Subjects who show progressive disease will be followed for survival and will no longer strictly adhere to study calendar. QOL questionnaires will be completed every 4 months until 1 year after treatment.

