# 6.1.4.5 Evaluation of Pathologic Fracture:

Any clinical suspicion of pathologic fracture will prompt radiologic evaluation with plain film, CT or MRI as appropriate and if confirmed by a radiologist, will constitute progression, unless it is at a treated site, in which case a treatment-related toxicity will be considered.

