#### Late Adverse Events

Adverse effects occurring in the time period from the end of acute monitoring, to 3 years post treatment for progression or death (whichever comes first), will be defined as late adverse events. These events will include all adverse events reported directly to a member of the study team and will be captured, assessed, graded and reported as appropriate.

In addition, the study team will review encounters in a select specialty category relevant to study endpoints. These select specialties include hospitalizations, medical oncology, and radiation oncology records and will be limited in scope based on categorization of events (GU/GI) and also the type of records that will be queried (hospitalizations, medical oncology, and radiation oncology).

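### The late-toxicity record review is limited to GU/GI events, so late injury in other organs can be missed unless it reaches the study team by another route

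*Combined protocol and SAP*

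**What the plan says.** Section 7.3 defines late adverse events as those arising after acute monitoring ends. The window runs to 3 years after treatment, with a clause on progression or death that is hard to parse. There are two sources:

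- Events reported directly to a study team member, in any organ.
- A record review, described as follows: "the study team will review encounters in a select specialty category relevant to study endpoints". The records are hospitalizations, medical oncology and radiation oncology, and the review "will be limited in scope based on categorization of events (GU/GI".

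The endpoint served is objective 2.2.7: "To evaluate the tolerability and toxicity of this regiment as measured according to CTCAE v4.0". Section 2.4.5 repeats the CTCAE basis. Neither names an organ system. No other section explains the GU/GI limit or extends the review to other organs.

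**The concern.** The search is tied to two organ groups, while the treatment is not. Inclusion criterion 3.1.8 asks only for one or more extracranial sites suitable for SABR. Section 4.1.3.1 gives planning instructions for skeletal, paraspinous, lung and liver lesions. Section 4.1.2 goes the other way for the gut: esophageal, gastric, intestinal or mesenteric disease is eligible only when no other lesion can be safely targeted. Sections 7.1.4 and 10.1 both say that SABR toxicity follows the treated location.

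The protocol also singles out late injuries that the filter leaves out. Section 4.1.3.2 discusses "The possibility that SBRT-induced fibrosis might cause occlusion of large central airways". Section 6.1.4.5 counts a confirmed pathologic fracture as progression "unless it is at a treated site, in which case a treatment-related toxicity will be considered". Hospital records of either event would be among those opened, but the event would fall outside the stated scope.

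A record review exists to find what visits and self-report miss. If it is blind to some organs, the late-toxicity figure for objective 2.2.7 can only be too low for those organs, never too high.

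**Working it through.** The plan states no figure on this point, so there is none to reproduce. Two things can be checked: how much of the protocol's own injury list lies outside GU/GI, and which capture routes remain for those injuries.

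**1. Share of listed injury types outside GU/GI**

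Input: the one-fraction table in section 4.1.3.2, with 26 serial and 4 parallel organ rows, so 26 + 4 = 30. Each row carries a grade 3 or higher endpoint. The documents do not define GU/GI, so the classes below are assumptions.

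- Strict class (9 rows): esophagus, stomach, duodenum, jejunum/ileum, colon, rectum, ureter, bladder wall, penile bulb.
- Broad class (9 + 4 = 13 rows): adds bile duct, liver, renal hilum and renal cortex.

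Share outside = (rows − GU/GI rows) / rows.

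| Rows counted | Broad class | Strict class |
|---|---|---|
| All 30 | (30 − 13)/30 = 17/30 = 57% | (30 − 9)/30 = 21/30 = 70% |
| Without optic pathway, cochlea, brainstem (27) | 14/27 = 52% | 18/27 = 67% |
| Also merging the two cord rows and the two lung rows (25) | 12/25 = 48% | 16/25 = 64% |

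The rows outside include myelitis, neuropathy, pericarditis, airway stenosis, pneumonitis, rib pain or fracture, skin ulceration and femoral head necrosis.

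**2. Routes left for a late non-GU/GI event**

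| Route | Organ limit | What it depends on |
|---|---|---|
| Toxicity evaluation at follow-up (5.4) | None | The visit taking place and the event being raised |
| Direct report (7.3) | None | The patient or a clinician telling the team |
| SAE reporting (7.4.3, 7.6, 7.6.1) | None | The team being aware of the event |
| Record review (7.3) | GU/GI only | Records opened by the team |

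The first three need the event to be brought to the team. Only the fourth can find an event that nobody mentioned, and it is the only one with an organ limit.

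**3. Size of the bias**

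Let M be the number of patients whose only late grade 3-5 event is non-GU/GI and appears only in records. The reported proportion with such an event is then too low by M/N. With N = 33 (maximum in section 11.2), each such patient moves it by 1/33 = 3.0 percentage points. With N = 38 (maximum in the Study Summary), the step is 1/38 = 2.6 points. The documents give no late event rates by organ and no figure for how often events escape the other routes, so M is unknown and the total cannot be computed.

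**The case against.** The strongest reply is that the review is only a supplement. The Time and Events table marks toxicity evaluation, history and examination, and CT of chest, abdomen and pelvis in every follow-up column, with no organ limit. Visits are every 8 weeks to month 8 and every 12 weeks to month 18. Section 4.4 keeps 12 weeks to two years and then four months; the table allows 3-6 months after month 18. A hospital stay of 24 hours or more meets the SAE definition, and SAEs go to the DSMC whatever the organ. This stands. It rules out the reading that late non-GU/GI toxicity goes uncollected. It does not close the gap, because each of these routes depends on the team hearing of the event.

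Three stronger inferences are tempting but not supported.

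- *The review would miss most late injuries.* The table counts injury types, not events. The majority also disappears (12 of 25) when cranial and duplicate rows are removed under the broad class.
- *Five of the example patient's six treated sites are outside GU/GI.* Section 4.1.1 lists "4 right axillary lymph nodes, L1-L2 bone metastasis, 3 right lung lesions, 1 left lung lesion, 2 liver lesions, and T2-T3 bone metastasis" to show how sites of disease are counted. It does not say which were irradiated, and the same section requires at least one site to be left untreated. Location is also a loose guide to the organ at risk: a lumbar or liver field can lie near kidney or bowel.
- *After progression the record review is the main source.* Section 4.4 does say "Subjects who show progressive disease will be followed for survival and will no longer strictly adhere to study calendar". But the late window in section 7.3 may itself close at progression, and then these patients are outside late capture altogether.

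**Conclusion.** The concern holds as a limited gap in ascertainment. The GU/GI restriction is unexplained, does not match an objective without organ limits, and leaves out about half to 70% of the injury types the protocol lists (17 of 30 on the broad class). Non-GU/GI events treated between visits and not reported to the team can be missed. The bias in the late-toxicity estimate is downward and its size is unknown. The primary endpoint is not affected.

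The conclusion assumes that the GU/GI wording is a limit rather than an example, which is its plain sense, and that the team follows it as written.

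A reader might also infer that the toxicity stopping rule becomes less likely to trigger. The documents do not allow that to be shown. The Stopping Rules section gives no threshold, and the rule draws on all grade 3-5 toxicity, including acute events, which section 7.3 collects without an organ limit.

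**What to change.** In section 7.3 (Late Adverse Events), delete the GU/GI restriction. Suggested text: *The study team will review hospitalization, medical oncology and radiation oncology records for CTCAE v4.0 grade 3-5 events in all organ systems.* This covers the same organ range as objective 2.2.7 and the same grades as the constraint-table endpoints. The current text sets no grade limit, so if lower-grade GU/GI events are now abstracted and the sponsor wants to keep them, say so.

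Separately, rewrite the sentence defining the late window so that it is clear whether capture ends at progression. This is a clarification and need not extend the window.

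The cost is small: the same three record types are used for at most 33 patients (section 11.2) or 38 (Study Summary), with slightly more abstraction time per chart. The reported late-toxicity rate may be higher.

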# 7.4 Definitions

# 7.4.1 Definition of Adverse Event

An adverse event (AE) is any untoward medical occurrence in a subject receiving study treatment and which does not necessarily have a causal relationship with this treatment. An AE can therefore be any unfavorable and unintended sign (including an abnormal laboratory finding), symptom, or disease temporally associated with the use of an experimental intervention, whether or not related to the intervention.

# 7.4.2 Severity of Adverse Events

All non-hematologic adverse events will be graded according to the NCI Common Terminology Criteria for Adverse Events (CTCAE) version 4.0. The CTCAE v4 is available at http://ctep.cancer.gov/reporting/ctc.html

If no CTCAE grading is available, the severity of an AE is graded as follows:

Mild (grade 1): the event causes discomfort without disruption of normal daily activities.

Moderate (grade 2): the event causes discomfort that affects normal daily activities.

Severe (grade 3): the event makes the patient unable to perform normal daily activities or significantly affects his/her clinical status.

Life-threatening (grade 4): the subject was at risk of death at the time of the event.

Fatal (grade 5): the event caused death.

# 7.4.3 Serious Adverse Events

A "serious" adverse event is defined in regulatory terminology as any untoward medical occurrence that:

# 7.4.3.1 Results in death.

If death results from (progression of) the disease, the disease should be reported as event (SAE) itself.

7.4.3.2	Is life-threatening. (the subject was at risk of death at the time of the event; it does not refer to an event that hypothetically might have caused death if it were more severe).
7.4.3.3	Requires in-patient hospitalization or prolongation of existing hospitalization for $\ge$ 24 hours.
7.4.3.4	Results in persistent or significant disability or incapacity.
7.4.3.5	Is a congenital anomaly/birth defect
7.4.3.6	Is an important medical event Any event that does not meet the above criteria, but that in the judgment of the investigator jeopardizes the subject, may be considered for reporting as a serious adverse event. The event may require medical or surgical intervention to prevent one of the outcomes listed in the definition of "Serious Adverse Event". For example: allergic bronchospasm requiring intensive treatment in an emergency room or at home; convulsions that may not result in hospitalization; development of drug abuse or drug dependency.

Note: A "Serious adverse event" is by definition an event that meets **any** of the above criteria. Serious adverse events may or may not be related to the research project. A serious adverse event determination does not require the event to be related to the research. That is, both events completely unrelated to the condition under study and events that are expected in the context of the condition under study may be serious adverse events, independent of relatedness to the study itself. As examples, a car accident requiring  $\geq$ 24 hour inpatient admission to the hospital would be a serious adverse event for any research participant; likewise, in a study investigating end-stage cancer care, any hospitalization or death which occurs during the protocol-specified period of monitoring for adverse and serious adverse events would be a serious adverse event, even if the event observed is a primary clinical endpoint of the study.

Pre-planned hospitalizations or elective surgeries are not considered SAEs. Note: If events occur during a pre-planned hospitalization or surgery, that prolong the existing hospitalization, those events should be evaluated and/or reported as SAEs.

 NCI defines hospitalization for expedited AE reporting purposes as an inpatient hospital stay equal to or greater than 24 hours. Hospitalization is used as an indicator of the seriousness of the adverse event and should only be used for situations where the AE truly fits this definition and NOT for hospitalizations associated with less serious events. For example: a hospital visit where a patient is admitted for observation or minor treatment (e.g. hydration) and released in less than 24 hours. Furthermore, hospitalization for pharmacokinetic sampling is not an AE and therefore is not to be reported either as a routine AE or in an expedited report.

#### 7.5 Unanticipated Problems Involving Risks to Subjects or Others (UPIRSOs):

The phrase "unanticipated problems involving risks to subjects or others" is found, but not defined in the HHS regulations at 45 CFR 46, and the FDA regulations at 21 CFR 56.108(b)(1) and 21 CFR 312.66. For device studies, part 812 uses the term

unanticipated adverse device effect, which is defined in 21 CFR 812.3(s). Guidance from the regulatory agencies considers unanticipated problems to include any incident, experience, or outcome that meets ALL three (3) of the following criteria:

 Unexpected in terms of nature, severity or frequency given (a) the research procedures that are described in the protocol-related documents, such as the IRB-approved research protocol and informed consent document; and (b) the characteristics of the subject population being studied;

#### AND

• Related or possibly related to participation in the research (possibly related means there is a reasonable possibility that the incident, experience, or outcome may have been caused by the procedures involved in the research);

#### AND

 Suggests that the research places subjects or others at greater risk of harm (including physical, psychological, economic, or social harm) than was previously known or recognized. Note: According to OHRP, if the adverse event is serious, it would always suggest a greater risk of harm.

#### Follow-up

All adverse events will be followed up according to good medical practices.

#### 7.5.1 Reporting

The UTSW IRB requires reporting of all UPIRSOs according to the guidance below. For participating centers other than UTSW, local IRB guidance should be followed for local reporting of serious adverse events. All SAEs occurring during the protocol-specified monitoring period should be submitted to the UTSW study team within 2 business days of the center learning of the event.

7.5.2 UPIRSOs occurring on the study require expedited reporting, and are submitted to the UTSW IRB through the UTSW eIRB by the UTSW study team and to the SCCC DSMC Coordinator. Hardcopies or electronic versions of the eIRB report; FDA Form #3500A forms, or other sponsor forms, if applicable; and/or any other supporting documentation available should be submitted to the UTSW study team and will be forwarded to the DSMC Coordinator. The DSMC Coordinator forwards the information onto the DSMC Chairman who determines if immediate action is required. Follow-up eIRB reports, and all subsequent SAE documentation that is available are also submitted to the DSMC Chair who determines if further action is required. (See Appendix IV of the SCCC DSMC Plan for a template Serious Adverse Event Form which may be utilized when a sponsor form is unavailable and SAE submission to the eIRB is not required).

All serious adverse events which occur on research subjects on protocols for which the SCCC is the DSMC of record require reporting to the DSMC regardless of whether IRB reporting is required. Hardcopies or electronic versions of the FDA Form #3500A forms, or other sponsor forms, if applicable; and/or any other supporting documentation available should be forwarded to the DSMC Coordinator.

If the event occurs on a multi-institutional clinical trial coordinated by the UTSW Simmons Cancer Center, the DOT Manager or lead coordinator ensures that all participating sites are notified of the event and resulting action, according to FDA guidance for expedited reporting. DSMC Chairperson reviews all serious adverse events upon receipt from the DSMC Coordinator. The DSMC Chairperson determines whether action is required and either takes action immediately, convenes a special DSMC session (physical or electronic), or defers the action until a regularly scheduled DSMC meeting. The following instructions section may be modified as needed to ensure clear guidance for institutions participating in the trial who will not report directly to the UTSW Institutional Review Board. If needed, this reporting may be facilitated by the UTSW study team for example.

Telephone reports to: (Investigator/study team: Insert names and phone numbers for required notifications)
Written reports to: (Investigator/study team: Insert names, fax numbers, an addresses for required notifications)
UTSW SCCC Data Safety Monitoring Committee Coordinator Email: [contact] [contact] or deliver to BLB.306
UTSW Institutional Review Board (IRB) Submit via eIRB with a copy of the final sponsor report as attached supporting

